9.8.3. Acute Systemic Allergic Reaction

Management of acute systemic allergic reactions will be at the discretion of the investigator, taking into account the following protocol procedures (see also [Table 2](#)), and should follow generally accepted medical standards.

Grade 1

A grade 1 acute systemic allergic reaction is defined as localized urticaria (wheals) with no medical intervention indicated.

Subjects may continue study treatment or have their study treatment interrupted at the investigator's discretion. The subject should be advised to contact the investigator immediately if there is any worsening of the pruritus, or if any systemic signs or symptoms develop. Antihistamines or topical corticosteroids or antipruritic agents may be prescribed as long as these are in line with the (dis)allowed medications as indicated in Section 8, Prestudy and Concomitant Therapy, or in the local Prescribing Information of the ARV agents.

Grade 2

A grade 2 acute systemic allergic reaction is defined as localized urticaria with medical intervention indicated, or mild angioedema with no intervention indicated.

Subjects may continue study treatment or have their study treatment interrupted at the investigator's discretion. If there is any worsening of the allergic reaction, the subject should be advised to contact the investigator immediately and to discontinue study treatment. Antihistamines or topical corticosteroids or antipruritic agents may be prescribed as supportive care as long as these are in line with the (dis)allowed medications as indicated in Section 8, Prestudy and Concomitant Therapy, or in the local Prescribing Information of the ARV agents.

Grade 3

A grade 3 acute systemic allergic reaction is defined as generalized urticaria, or angioedema with intervention indicated or symptoms of mild bronchospasm.

Subjects will permanently discontinue study treatment. Subjects will be treated as clinically appropriate. Standard management should be undertaken.

Grade 4

A grade 4 acute systemic allergic reaction is defined as acute anaphylaxis, or life-threatening bronchospasm, or laryngeal edema.

Subjects will permanently discontinue study treatment. Subjects will be treated as clinically appropriate. Standard management should be undertaken.

Table 2: Summary of Allergic Reaction Follow-up

DAIDS Toxicity Grade	Definitions	Investigator Action
Grade 1	Localized urticaria (wheals) with no medical intervention indicated	Subject may continue study treatment
Grade 2	Localized urticaria with intervention indicated, or mild angioedema with no intervention indicated	Subject may continue study treatment
Grade 3	Generalized urticaria, or angioedema with intervention indicated, or symptoms of mild bronchospasm	Permanently discontinue study treatment
Grade 4	Acute anaphylaxis, or life-threatening bronchospasm, or laryngeal edema	Permanently discontinue study treatment

9.8.4. Potential Renal Toxicity

Estimated glomerular filtration rate for creatinine clearance ($eGFR_{\text{creatinine}}$ calculated according to the MDRD formula) will be followed postbaseline during the treatment phase.

Any subjects who have an $eGFR_{\text{creatinine}}$ of <50 and a decrease of 20% in $eGFR_{\text{creatinine}}$ from baseline, or who have other clinical and/or laboratory evidence of acute renal failure will be discussed with the sponsor's medical monitor and may permanently discontinue study treatment.

The eGFR calculations will be performed and provided to the investigator by the central laboratory.

Subjects with negative or trace proteinuria at baseline who develop >1+ proteinuria on urinalysis must have urinalysis repeated, with a concurrent urine chemistry, within 2 weeks of receipt of results. Upon confirmation of proteinuria, subjects will be asked to return to the site for a scheduled or unscheduled follow-up visit. It is recommended that the investigator contacts the sponsor's medical monitor to discuss if further consultation with a nephrologist is clinically warranted.

Once an individual subject has developed any of these renal changes and the above management guidelines have been applied, it is not necessary to further unscheduled repeat evaluations if it is determined that it is safe for the subject to continue on treatment with standard visits as described in the protocol.

9.8.5. Potential Posterior Uveitis Cases

In a 9-month toxicology study conducted in dogs, some animals administered the highest dose of TAF (12 to 18 mg/kg) had minimal mononuclear cell infiltration in the posterior uvea, considered secondary to general debilitation; this finding did not occur in animals given lower doses and it has not occurred in other animal studies. This preclinical finding has also not been observed in humans where the dose is much lower, nor have there been reports of posterior uveitis in human clinical studies. Nonetheless, if subjects develop signs or symptoms of posterior uveitis, which include notable eye pain or redness, reduced visual acuity, or "floaters", investigators in this study should inform the sponsor's medical monitor and determine, based on their medical judgment, the need for ophthalmologic evaluation including dilated funduscopy, and if required, optical coherence tomography.

9.8.6. Hyperglycemia

Grade 3: 13.89 to 27.75 mmol/L (250-500 mg/dL)

Grade 4: >27.75 mmol/L (>500 mg/dL)

Toxicity management decisions should be based on fasted results. If elevated glucose levels are from a nonfasted blood draw, the draw must be repeated after an 8-hour fast.

Subjects who experienced asymptomatic glucose elevations of grade 3 and subjects with pre-existing diabetes who experienced asymptomatic glucose elevations of grade 4 may continue study treatment unless clinical assessment foresees an immediate health risk to the subject. Appropriate clinical management of hyperglycemia must be started in a timely fashion if applicable. Subjects with persistent grade 3 or 4 glucose elevations despite appropriate anti-hyperglycemic treatment should permanently discontinue study treatment.

9.8.7. Hypertriglyceridemia and Hypercholesterolemia

Hypertriglyceridemia: Grade 3: 5.7 to 11.4 mmol/L (>500-1,000 mg/dL)

Grade 4: >11.4 mmol/L (>1,000 mg/dL)

Hypercholesterolemia: Grade 3: \geq 7.77 mmol/L (>300 mg/L)

Grade 4: Not applicable

Toxicity management decisions should be based on fasted results. If elevated lipid levels are from a nonfasted blood draw, the draw must be repeated after an 8-hour fast.

Subjects who experienced asymptomatic triglyceride or cholesterol elevations of grade 3 or 4 may continue study treatment unless clinical assessment foresees an immediate health risk to the subject.

Hypertriglyceridemia and hypercholesterolemia should be treated according to the specific guidelines for treating HIV-positive subjects (see [Attachment 5](#)). Current treatment guidelines specify different lipid thresholds for intervention for different degrees of cardiovascular risk. The presence or absence of other significant cardiovascular risk factors, which include smoking, age, family history of premature cardiovascular disease, diabetes, hypertension, low high-density lipoprotein (HDL), and prior history of cardiovascular disease should be taken into account. Appropriate clinical management of hyperlipidemia in the setting of HIV should be started in a timely fashion if applicable, and taking into account the disallowed medications (refer to [Section 8](#), Prestudy and Concomitant Therapy).

9.8.8. Lipodystrophy/Fat Redistribution/Body Changes

Investigators are requested to avoid using the term ‘lipodystrophy acquired’ or ‘fat redistribution’ to describe and report body fat abnormalities, as these terms are not descriptive nor fully accurate. The different symptoms and gradings are listed in the DAIDS grading table ([Attachment 2](#)) under Endocrine/Metabolic. The following terms are included: lipohypertrophy, lipoatrophy, and gynecomastia.

Although metabolic abnormalities such as hyperlipidemia or hyperglycemia are often associated with body changes, these events should be recorded separately at adverse event reporting.

9.9. Sample Collection and Handling

Blood samples drawn will be frozen and stored. These stored samples may be used by the sponsor or its research partners for HIV-1 genotype/phenotype assays, for retesting the amount of HIV-1 RNA in the blood, for additional measurement of antiviral drug levels in the blood, clinical laboratory testing to provide additional safety data, or future testing to learn more about how the investigational drug has worked against HIV-1. Additionally, pharmacokinetic analyses for DRV and COBI may be performed for those subjects experiencing virologic failure at the request of the sponsor. No human genetic testing will be performed on these samples. See also [Section 16.2.5](#).

In addition, PBMCs will be isolated from whole blood at the central laboratory and stored for future analysis if needed.

The actual dates and times of sample collection must be recorded in the eCRF or laboratory requisition form. See the [Time and Events Schedule](#) for the timing and frequency of all sample collections.

Instructions for the collection, handling, storage, and shipment of samples are found in the laboratory manual that will be provided. Collection, handling, storage, and shipment of samples must be under the specified, and where applicable, controlled temperature conditions as indicated in the laboratory manual.

10. SUBJECT COMPLETION/DISCONTINUATION OF STUDY TREATMENT/ WITHDRAWAL FROM THE STUDY

10.1. Completion

In the period up to Week 48, a subject will be considered to have completed the main study period if he or she has continued study medication intake up to Week 48 and has completed assessments at Week 48. Subjects who prematurely discontinue study treatment for any reason before completion of the 48-week treatment period will not be considered to have completed the main study period.

In the period after Week 48, subjects will be considered to have completed the extension period if he or she continued study medication intake until D/C/F/TAF becomes commercially available and is reimbursed, or can be accessed through another source, or until the sponsor terminates clinical development and has completed assessments until that point. Subjects who prematurely discontinue study treatment for any reason before that point, will not be considered to have completed the extension period.

10.2. Withdrawal From the Study

A subject will be automatically withdrawn from the study for any of the following reasons:

- Lost to follow-up
- Withdrawal of consent
- Discontinuation of study treatment for any reason
- Subject request to stop study treatment for any reason.

A subject's study treatment **must** be discontinued if:

- The investigator or sponsor believes (eg, that for safety or tolerability reasons (eg, adverse event) it is in the best interest of the subject to discontinue treatment
- The subject becomes pregnant
- The subject meets any of the safety stopping rules (see Section 3.1, Overview of Study Design)

- The subject meets any of the resistance stopping rules (see Section 3.1, Overview of Study Design)
- The subject experiences unacceptable toxicity (as defined in Section 9.8, Toxicity Management)
- The subject develops clinical hepatitis
- Prolonged temporary study treatment discontinuation >4 consecutive weeks
- The study is discontinued at the request of the sponsor, concerned regulatory agency, or Independent Ethics Committee/Institutional Review Board (IEC/IRB)

A subject's study treatment **may** be discontinued if:

- A serious adverse event occurs
- The subject fails to comply with the protocol or study staff requirements
- Intercurrent illness that would, in the judgment of the investigator, affect assessments of clinical status to a significant degree
- The subject starts disallowed treatment, or requires new onset treatment with one of the disallowed medications (please refer to Section 8, Prestudy and Concomitant Therapy)
- The subject experiences protocol-defined virologic failure, shows resistance to study drug(s) upon genotypic and phenotypic resistance testing, and the investigator makes the decision to discontinue study treatment
- The subject experiences persistent HIV-1 RNA ≥ 400 copies/mL after Week 24, that does not meet the protocol-defined virologic failure criteria, but shows resistance to study drug(s) upon genotypic and phenotypic resistance testing, and the investigator makes the decision to discontinue study treatment

Protocol-defined virologic failure is not considered a stopping rule.

If the investigator considers withdrawing a subject from study treatment for one of the above reasons, he/she should contact the sponsor for further discussion and final decision, unless the medical condition requires immediate action that cannot wait contact with the sponsor.

Subjects who prematurely discontinue study treatment during the open-label treatment period will be required to complete ESTD assessments as soon as possible but no later than 1 week of discontinuing study treatment.

In addition, a follow-up visit is required for any subject who has an ongoing adverse event or serious adverse event at the time of his/her last study visit. These subjects are required to return to the site 30 days (± 7 days) after completion of the last study-related visit (unless consent is withdrawn).

Investigators will refer subjects discontinuing therapy for any reason before Week 48 for follow-up care, either at a clinic associated with the investigator or an external care facility according to subject preference. To assess whether subjects have been retained in care, investigators will be

asked to monitor subject's engagement with the referral site. Retention in care will be defined as having a documented office visit within 90 days of discontinuing the study drug before Week 48. Subjects who complete the study through Week 48 will not be monitored for retention in care.

If a subject is lost to follow-up, every reasonable effort must be made by the study site personnel to contact the subject and determine the reason for discontinuation/withdrawal. The measures taken to follow up must be documented.

When a subject withdraws before completing the study, the reason for withdrawal is to be documented in the eCRF and the source document. Study drug dispensed to the withdrawn subject may not be dispensed to another subject (unless the bottles are unopened). Subjects who withdraw will not be replaced.

10.3. Withdrawal From the Use of Research Samples

Withdrawal From the Use of Samples in Future Research

The subject may withdraw consent for use of samples for research (refer to Section 16.2.5, Long-Term Retention of Samples for Additional Future Research). In such a case, samples will be destroyed after they are no longer needed for the clinical study. Details of the sample retention for research are presented in the main ICF.

11. STATISTICAL METHODS

Statistical analysis will be done by the sponsor or under the authority of the sponsor. A general description of the statistical methods to be used to analyze the efficacy and safety data is outlined below. Specific details will be provided in the Statistical Analysis Plan.

The following analyses will be performed:

- The interim analysis: once all subjects have been assessed for safety at Day 3, and for resistance stopping rules at Week 4.
- The primary analysis: once all subjects have completed the Week 48 assessments and the 30-day follow-up visit (if applicable), or discontinued earlier.

11.1. Analysis Sets

The following analysis sets will be used and are defined:

- Intent-to-treat (ITT) population: all subjects who have received at least one dose of study drug.
- Per-protocol population: ITT population without major protocol deviation that is considered to have an impact on the safety or efficacy assessments.

11.2. Subject Information

Subject information will be analyzed based on the ITT population, unless otherwise specified.

For all subjects who receive at least 1 dose of study drug descriptive statistics will be provided.

11.3. Sample Size Determination

The primary efficacy endpoint is the proportion of subjects who have HIV-1 RNA <50 copies/mL at Week 48 as defined by the FDA snapshot analysis (ITT). As this is an exploratory study with no formal hypothesis testing on the primary endpoint, no formal sample size calculation was performed. With a sample size of 100 subjects and an expected virologic response rate ranging from 60-80%, the exact corresponding 95% confidence intervals (CIs) are: 60% (49.7%, 69.7%), 70% (60.0%, 78.8%), and 80% (70.8%, 87.3%). The half-width of the exact corresponding 2-sided 95% CI is 10.0%, 9.4%, and 8.3%, respectively, and is therefore less than 10% across the range of expected outcomes which is the desired precision. Additionally, with a sample size of 100 subjects, the probability to observe an adverse event with a true incidence of 1% or 4% is 63% and 98% respectively.

11.4. Efficacy Analyses

11.4.1. Antiviral Efficacy and Immunologic Change

The primary efficacy endpoint is the proportion of subjects who have HIV-1 RNA <50 copies/mL at Week 48 as defined by the FDA snapshot analysis (ITT).

Virologic suppression (HIV-1 RNA <50 copies/mL) will also be analyzed as secondary endpoints at Week 24 and Week 48 according to the below analyses:

- FDA Snapshot algorithm in the ITT and Per-Protocol population
- Time to loss of virological response (TLOVR) algorithm in the ITT population

Virologic decay will be reported as the mean \log_{10} change in HIV-1 viral load from baseline to Weeks 2, 4, 8, 12, and 24 as part of the interim analysis as a secondary endpoint.

The proportion of subjects experiencing protocol defined virologic failure at Week 24 and Week 48 will be tabulated using descriptive statistics along with the 95% CIs. The Wilson (Score) method for the CI will be used.

The changes from baseline in CD4⁺ cell count at Weeks 12, 24, and 48 will be summarized using descriptive statistics.

11.4.2. Resistance Determinations

The number of PR mutations (including IAS-USA primary and secondary PI RAMs), RT mutations (including IAS-USA N[t]RTI RAMs and IAS-USA non-nucleoside RT inhibitor [NN(t)RTI] RAMs), and INI mutations (including IAS-USA primary and secondary INI-RAMS) present will be tabulated based on resistance tests performed at the screening/baseline visit.

The proportion of subjects meeting resistance stopping rules, requiring discontinuation of study drug, based on the findings of screening/baseline resistance testing will be tabulated as part of the interim analysis.

HIV-1 genotype/phenotype will be analyzed from samples of subjects with protocol-defined virologic failure and with HIV-1 RNA ≥ 400 copies/mL.

The number of treatment-emergent PR mutations (including IAS-USA primary and secondary PI RAMs) and RT mutations (including IAS-USA N(t)RTI RAMs and IAS-USA NNRTI RAMs), as well as specific mutations associated with resistance to DRV, FTC, and TAF will be tabulated based on the observed virologic failures through the study period.

Fold change (FC) in 50% effective concentration (EC₅₀) of ARVs will be tabulated. Loss of phenotypic susceptibility may be analyzed dependent on the number of virologic failures and phenotypes available through the study period.

11.5. Medical Resource Utilization and Health Economics Analyses

All-cause and HIV-specific HRU during the study period will be summarized overall and by category as the counts per patient per month (PPPM). Monthly average counts per subject will also be calculated to show the temporal trend for each category.

Costs of care will be calculated by assigning costs based on Centers for Medicare & Medicaid Services (CMS) fee schedule to assessed HRU on a per subject per month basis. Descriptive statistics will be calculated to compare the costs of care from baseline to Weeks 12, 24, and 48.

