Phase	Day 1 Screening/ Baseline ^b	Open-label Treatment Phase									ESTD (Early Study Treatment Discontinuation) Visit ^e	30-day Follow-up ^f	90-day Follow-up	
		Day 3 Safety Assessment ^c	Main Study Period						Extension Period ^d					
			Week ^a											
			2	4	8	12	24	36	48					
Study Procedures														
Screening/Administrative														
Informed consent process ^g	X													
Demographic information	X													
Medical history ^h	X													
HIV history	X													
Inclusion/exclusion criteria	X													
Determine Continued Eligibility (by Investigator)														
Formal review of central screening/baseline safety laboratory tests by investigator (no scheduled clinic visit)		X												
Formal review of screening/baseline HIV genotypic drug resistance testing by investigator				X ⁱ										
Study Drug Administration														
Dispense study drug ^j	X			X	X	X	X	X	X ^k	X ^k				
Drug accountability (pill count) ^l				X	X	X	X	X	X	X	X			
Adherence (subject self-report) ^m				X	X	X	X	X	X	X	X			
Efficacy Assessments														
HIV-1 RNA ⁿ	X		X	X	X	X	X	X	X	X	X	X		
CD4 ⁺ /CD8 ⁺	X			X	X	X	X	X	X	X	X			
Combined Genotype/Phenotype ^o	X ^p		X	X	X	X	X	X	X	X	X			
Safety Assessments														
Vital signs, body weight and height ^q	X		X	X	X	X	X	X	X	X	X	X		
Full physical examination ^r	X								X	X	X			
Symptom-directed physical examination ^r			X	X	X	X	X	X		X		X		
Review concomitant medications	X		X	X	X	X	X	X	X	X	X	X		
Adverse events assessment ^s	X		X	X	X	X	X	X	X	X	X	X		

Phase	Day 1 Screening/ Baseline ^b	Open-label Treatment Phase									ESTD (Early Study Treatment Discontinuation) Visit ^e	30-day Follow-up ^f	90-day Follow-up	
		Main Study Period												Extension Period ^d
		Week ^a												
		Day 3 Safety Assessment ^c	2	4	8	12	24	36	48					
Study Procedures														
Health Outcome Assessments														
Medical resource utilization			X	X	X	X	X	X	X	X	X ^u	X		
HIV Treatment Satisfaction Questionnaire (HIVTSQs) ^t				X				X		X	X ^u			
Clinical Laboratory Assessments														
Hepatitis B/C serology	X													
Estimated glomerular filtration rate (eGFR)	X		X	X	X	X	X	X	X	X	X	X		
Genotype ^v	X													
Pregnancy test ^w	X		X	X	X	X	X	X	X	X	X	X		
Hematology	X ^x		X ^x	X ^x	X	X ^x	X	X	X	X ^x	X	X		
Chemistry	X		X	X	X	X	X	X	X	X	X	X		
Serum amylase/lipase ^y	X													
Urinalysis ^z	X		X	X	X	X	X	X	X	X	X	X		
Other														
Retention in care assessment													X ^{bb}	

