Retesting of abnormal screening/baseline safety laboratory values noted above will be allowed once. Retesting will take place during an unscheduled visit.

The investigator will review the ARV screening/baseline resistance data at Week 4 ± 7 days or sooner, depending on the availability of the screening/baseline HIV genotypic drug resistance testing results from the central laboratory. Subjects who do not show full sensitivity to all drugs in the FDC study regimen according to the susceptibility assessment in the GenoSure Prime[®] report will be contacted to return to the study site for ESTD. Subjects with identified resistance to lamivudine/FTC, attributed to the presence of the M184I/V mutation alone will be permitted to remain in the study.

Subjects will be treated for 48 weeks in the main study period and will return to the site for visits at Weeks 2, 4, 8, 12, 24, 36, and 48. Assessment of drug accountability and reasons for non-adherence, and recording of concomitant therapies, adverse events, vital signs (including the subject's body weight), and physical examinations (complete or symptom-directed) will be performed at each visit from baseline onwards. Laboratory evaluations for efficacy and safety (HIV-1 viral load, biochemistry, hematology, and urinalysis) will be performed at all study visits. CD4⁺/CD8⁺ cell count will be assessed at Weeks 4, 8, 12, 24, 36, and 48. Patient-reported outcome (PRO) measures will be assessed at Weeks 4, 24, and 48 using the validated 10-item HIVTSQs (Version 2006)¹² ([Attachment 7](#)). Medical resource utilization data will be collected from all subjects throughout the main study period.

Subjects who are on study drug and who experience a protocol-defined virologic failure (see below) will undergo genotypic and phenotypic resistance testing, preferably at the time of the confirmed virologic failure visit if the HIV-1 RNA is ≥ 400 copies/mL. If resistance testing is not able to be performed at the time of confirmed virologic failure, resistance testing may be

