
Toxicity Management

The combination of D/C/F/TAF is not anticipated to exacerbate known toxicities or lead to new toxicities. Measures and guidelines for the monitoring and management of specific toxicities with DRV, COBI, FTC, or TAF are included in Section 9.8 of this protocol. The presented toxicity management guidelines are applicable throughout the entire study starting from baseline through the 48-week main study period and through the extension period (or ESTD and an additional follow-up visit, if applicable).

Medical Resource Utilization and Health Economics Data Collection

Treatment of HIV-1 infection with D/C/F/TAF may result in a change in medical resource utilization from baseline over the duration of the study.

Medical resource utilization data as defined in Section 9.4 will be collected throughout the main study period. Additionally, costs will be assigned to type of HRU to calculate a per subject per

month cost associated with the initiation and maintenance of ART. These outcome measures are being examined as part of this study to ensure they are captured as accurately as possible, in a prospective fashion. Previous retrospective data have demonstrated a decrease in overall medical resource utilization with the initiation of a boosted-darunavir based regimen.⁴⁵ While there is no comparator arm in this study, the inclusion of these endpoints as part of this study will help describe if similar observations are seen in a prospective cohort starting treatment on D/C/F/TAF. The data can also provide input for future economic modeling analysis.

Similarly, this study aims to describe changes in PRO assessed by the 10-item HIVTSQs throughout the main study period (ie, Weeks 4, 24, and 48). Satisfaction with HIV therapy is being evaluated more frequently in HIV clinical studies. The HIVTSQ was designed specifically to measure satisfaction with medication for people infected with HIV.^{43,44} In FLAMINGO, an open-label comparative study of DRV and DTG in combination with NRTIs, improvements in HIVTSQ score from baseline was observed over a 48-week period.⁶ While this study itself is non-comparative, the aim is to describe changes in patient satisfaction as a result of starting treatment with D/C/F/TAF.

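### The protocol speaks of change from baseline in resource use and cost, and of satisfaction changing because treatment began, but schedules no pre-treatment value for total use, cost or satisfaction

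*Protocol*

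**What the plan says.** **Resource use and cost, rationale (Protocol 3.2).** Treatment with the study drug "may result in a change in medical resource utilization from baseline over the duration of the study". The section then cites retrospective data showing lower overall resource use when a boosted-darunavir regimen was begun. It says these endpoints will help describe whether something similar is seen prospectively, while noting that there is no comparator arm.

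**Resource use and cost, analysis (Protocol 11.5).** "Costs of care will be calculated by assigning costs based on Centers for Medicare & Medicaid Services (CMS) fee schedule to assessed HRU", per subject per month. Then: "Descriptive statistics will be calculated to compare the costs of care from baseline to Weeks 12, 24, and 48". The same section also plans on-study counts per patient per month and monthly averages to show the trend.

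**Resource use, collection.** Section 3.1: "Medical resource utilization data will be collected from all subjects throughout the main study period". Section 9.4 lists four components: hospitalizations, outpatient visits, emergency room visits, and medications taken from the Concomitant Medication page. In the Time and Events Schedule the row "Medical resource utilization" is blank at Day 1 and Day 3 and is first marked at Week 2.

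**Satisfaction.** Section 3.1: "Patient-reported outcome (PRO) measures will be assessed at Weeks 4, 24, and 48". Section 3.2 gives two aims. One is to describe changes across those three visits. The other reads: "the aim is to describe changes in patient satisfaction as a result of starting treatment with D/C/F/TAF". Section 11.8 plans absolute values and changes where applicable, and names no reference visit.

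**The concern.** A change from baseline needs a baseline value. A decrease on starting a regimen needs a value from before the start. If the protocol sets out to describe such changes but first collects the data after dosing has begun, no later analysis plan can supply what is missing.

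The practical risk is substitution. Without a pre-treatment period, the first weeks on study become the reference by default. Those weeks have the densest visit schedule, so a later decline could be reported as a change from baseline when it partly reflects the study calendar. For satisfaction, the risk is that a rise or fall after Week 4 is described as the effect of starting treatment, although every scheduled score was obtained after treatment started.

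**Working it through.** No figure in the protocol is at issue, so the check sets the stated aims against what the schedule collects.

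**Step 1. Pre-treatment collection, component by component.** Sources: Time and Events Schedule; Sections 3.1, 8 and 9.4.

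| Measure | Day 1 mark | Look-back stated | Pre-treatment value |
|---|---|---|---|
| Hospitalizations | no | none | no |
| Outpatient visits | no | none | no |
| Emergency room visits | no | none | no |
| Medications | yes (concomitant medication review) | 30 days before first dose (Section 8) | yes |
| HIVTSQs | no; first at Week 4 | not applicable | no |

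Three of the four resource-use components have no pre-treatment value.

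**Step 2. Consequence for cost.** Section 11.5 builds cost only from assessed resource use. Baseline total cost would be the sum of four component costs, three of which are unobserved. It cannot be formed, so neither can a difference from it. A medication-only cost before and after could be formed.

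**Step 3. What the data do support.** Counts per patient per month and monthly averages from Week 2 onward need no pre-treatment value. The secondary objective in 2.1.1 (resource use, cost and their time trends through Week 48) and the endpoints in 2.1.2 can be delivered from these data.

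**Step 4. Satisfaction.** Scheduled main-period scores fall at Weeks 4, 24 and 48, plus the early-discontinuation visit. Available changes are Week 24 minus Week 4 and Week 48 minus Week 4. A change from before treatment is not available. Nor would a Day 1 score help: the questionnaire in Attachment 7 asks about current treatment, and inclusion criterion 4 admits only treatment-naïve subjects (apart from prior pre-exposure prophylaxis).

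**Step 5. The visit calendar as a source of apparent decline.** Post-Day-1 scheduled visits, from Section 3.1:

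- Day 1 to Week 12: Weeks 2, 4, 8, 12 = 4 visits in 12 weeks.
- Weeks 12 to 24: Week 24 = 1 visit in 12 weeks.
- Weeks 24 to 48: Weeks 36 and 48 = 2 visits in 24 weeks = 1 per 12 weeks.

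Fall in scheduled contacts = 1 − 1/4 = 75%. On the protocol's monthly scale, 12 weeks = 84 days, and 84 / (365/12) = 2.76 months. The rate goes from 4/2.76 = 1.45 to 1/2.76 = 0.36 visits per subject per month. This counts scheduled protocol visits only. It would enter the utilization or cost results only if those visits were counted as outpatient visits, and neither 9.4 nor 11.5 says whether they are.

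**The case against.** The strongest reply is that the objectives and endpoints ask for nothing before treatment. Section 2.1.1 speaks of trends through 48 weeks, 2.1.2 of use during the main study period and mean HIVTSQs scores at three visits, and 11.5 of on-study counts. All of that is feasible, and this part of the reply stands in full.

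The cost sentence in 11.5 can also be read as cost accrued over intervals that begin at baseline and end at Weeks 12, 24 and 48, which on-study data would support. That reading is possible. The verb *compare* and the per-month scale sit awkwardly with it, but the sentence taken alone is ambiguous rather than impossible. It does not rescue 3.2, where a change in utilization from baseline is stated outright and linked to a decrease seen on starting treatment.

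On satisfaction, 11.8 promises no comparison with a pre-treatment score, and the missing Day 1 questionnaire is sound design. What remains is the closing causal phrase in 3.2.

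A reader might infer three stronger things that the documents do not support:

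- **That no resource-use data exist before treatment.** Medications do have a pre-dose record.
- **That the planned analyses in 11.5 and 11.8 cannot be done.** The monthly counts, the trends and the changes from Week 4 all can.
- **That a 75% fall is built into utilization or cost.** It is built into the visit calendar. Whether it reaches the outcomes depends on a counting rule the protocol does not state.

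Finally, interval choice and reference visits are often left to the analysis plan. That is fair for those details, but an analysis plan cannot create pre-treatment data.

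**Conclusion.** The point holds in limited form. A change from pre-treatment in total resource use or total cost cannot be computed, because hospitalizations, outpatient visits and emergency room visits have no pre-treatment value for any of the approximately 100 subjects. A change in satisfaction caused by starting treatment cannot be described either. On-study trends and changes from Week 4 are unaffected.

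This rests on two readings: that the blank Day 1 and Day 3 cells in the resource-use row mean no collection, and that the absence of a stated recall period means none is intended. If the case report form does carry a look-back, the protocol should say so and the resource-use part of the point falls away.

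The severity is minor. These are descriptive secondary outcomes in a single-arm study with no hypothesis test. The primary endpoint and the safety evaluation are not touched.

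**What to change.** **Resource use and cost: choose one.**

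1. Add a short Day 1 case report form item on hospital, emergency room and outpatient use over a defined prior period, for example 3 months. The cost is one form item and some recall error. Because diagnosis must fall within 2 weeks of the baseline visit, the look-back will also contain diagnostic contacts and should be interpreted with that in mind. Subjects already enrolled would have to be asked in retrospect.
2. Restate 3.2 and 11.5 as on-treatment trends in use and cost per subject per month over named intervals (Day 1 to Week 12, Weeks 12 to 24, Weeks 24 to 48), and drop the claim of change from baseline. The cost is wording only.

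**In either case,** state in 9.4 or 11.5 that protocol-mandated visits are excluded from outpatient counts and cost, so that the visit calendar cannot produce a decline.

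**Satisfaction.** Name Week 4 as the HIVTSQs reference visit in 11.8, and remove from 3.2 the words that attribute the change to starting treatment. Do not add a Day 1 questionnaire. The cost is wording only.
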